10.3 Responsibilities of the investigator and IRB/IEC

The protocol and the proposed informed consent form must be reviewed and approved by a properly constituted IRB/IEC/REB before study start. A signed and dated statement that the protocol and informed consent have been approved by the IRB/IEC must be given to Novartis before study initiation. Prior to study start, the investigator is required to sign a protocol signature page confirming his/her agreement to conduct the study in accordance with these documents and all of the instructions and procedures found in this protocol and to give access to all relevant data and records to Novartis monitors, auditors, Novartis clinical quality assurance representatives, designated agents of Novartis, IRBs/IECs/REBs, and regulatory authorities as required. If an inspection of the clinical site is requested by a regulatory authority, the investigator must inform Novartis immediately of this request.

10.4 Publication of study protocol and results

Novartis assures that the key design elements of this protocol will be posted in a publicly accessible database such as clinicaltrials.gov. In addition, upon study completion and finalisation of the study report the results of this study will be either submitted for publication and/or posted in a publicly accessible database of clinical study results.

11 Protocol adherence

Investigators ascertain they will apply due diligence to avoid protocol deviations. Under no circumstances should the investigator contact Novartis or its agents, if any, monitoring the study to request approval of a protocol deviation, as no authorised deviations are permitted. If the investigator feels a protocol deviation would improve the conduct of the study this must be considered a protocol amendment, and unless such an amendment is agreed upon by Novartis and approved by the IRB/IEC it cannot be implemented. All significant protocol deviations will be recorded and reported in the clinical study report.



References will be made available on request.

13 Appendix 1: Clinically notable laboratory values and vital signs

Laboratory notable range deviations will be provided in the investigator binder.

Table 13-1 Vital signs notable range deviations

Vital signs		Notable abnormalities
Pulse (beats/min)		either ≥ 120 + increase $\geq 25^*$ or > 130 either ≤ 50 + decrease $\geq 30^*$ or < 40
Blood pressure (mmHg)	systolic	either ≥ 180 + increase $\geq 30^*$ or > 200 either ≤ 90 + decrease $\geq 30^*$ or < 75
	diastolic	either ≥ 105 + increase $\geq 20^*$ or > 115 either ≤ 50 + decrease $\geq 20^*$ or < 40
Weight		a weight change of $> 10\%$ during the study

* Refers to post-BL value as compared to BL value.

14 Appendix 2: testing for patients with elevated LFTs

At the first recognition of a liver related AE an immediate blood draw for items listed on Panel A (see below) must be performed. After timely consultation with a gastroenterologist or hepatologist, Panel B below may need to be drawn.

If jaundice is present right upper quadrant ultrasound with Doppler within 24-72h should be performed.

Liver panel A must be performed within 24h of the abnormal LFTs

A urine sample must be collected for toxicology screen. Human immunodeficiency virus status must be established.

A blood sample must be draw for:

- HBsAg, hepatitis B core antibody (HbcAb), Hepatitis C RNA.
- HAV total and immunoglobulin M (IgM).
- Hepatitis E serology: IgM and immunoglobulin G.
- Herpes simplex virus, cytomegalovirus & Epstein-Barr virus serology.

Liver panel B – may be required following consultation with a specialist

After a refreshed history, physical examination, and upon consultation with a gastroenterologist or hepatologist, tests might include:

- Autoimmune disease: antinuclear antibody (ANA), anti-smooth muscle antibody (ASMA), anti-liver-kidney microsomal antibody (anti-LKM-1), antibodies against soluble liver antigen (anti-SLA), antibodies to liver-specific asialo-glycoprotein receptor, anti-mitochondrial antibody (AMA).
- Other infectious disease: malaria, tuberculosis, parasites, West Nile virus.
- Wilson’s disease: serum ceruloplasmin.
- Hemochromatosis genotype (C282Y, H63D mutations).
- α -1 anti-trypsin level, and if low then phenotype.

- Tests for hemolysis (LDH, peripheral smear, haptoglobin, reticulocyte count).
- Liver biopsy.

Clinical Development

LAF237/Galvus

Clinical Study Protocol CLAF237A23156 / NCT01528254

A 5-year study to compare the durability of glycemic control of a combination regimen with vildagliptin & metformin versus standard-of-care monotherapy with metformin, initiated in treatment-naïve patients with type 2 diabetes mellitus

RAP Module 3 – Detailed Statistical Methodology

Author: [REDACTED], Novartis Trial Statistician
[REDACTED], [REDACTED] Trial Statistician

Document type: RAP Documentation

Document status: Final V3.0

Release date: 7 May 2019

Number of pages: 41

May not be used, divulged, published or otherwise disclosed
without the consent of Novartis

Document History – Changes compared to previous version of RAP module 3.

Version	Date	Changes
2.2	28NOV2018	
Section 2.1.5 - Background and demographic characteristics – baseline HbA1c categories were updated to be <7% and >=7%.
 
2.2.1 - Definition of geographic region for efficacy analyses – geographic region categories were added as per Novartis decision.
 
2.2.2.3 – Rate of loss in glycemc control over time – time (of HbA1c measurements, in years) added as random effect to the analysis model.
 
2.3.1 - Overall experience of adverse events (AEs) – statement added that AEs will be analyzed by study period as well in addition to overall (including study events from study period 1, 2 and 3) in line with DMC analyses.
 
Section 2.3.1.1 – statement added that AEs will be analyzed by study period for all subsection of AEs leading to discontinuation.
 
Section 2.3.5 - Hypoglycemic events – statement added that events will be analyzed by study period as well in addition to overall in line with DMC analyses. Added new category to plasma glucose level list.
 
Section 2.8 – Added statement that time will be used as both a fixed and random effect in analyses of rate of loss of glycemc control.
 
Section 2.8 - Changes in the conduct of the study or planned analyses – it was added that the definition of initial treatment failure is changed to regard the date of the second of the two consecutive measurements of HbA1c values >=7%.

3	06May2019	
Section 1.4 Changed duration derivation from weeks to Months.
 
Section 1.6 Added the list of AEs of special interest
 
Section 2.1.2 Added information of efficacy parameters to be considered for deviation code N02 and N03.
 
Section 2.1.5 Removed definition of baseline HbA1c and FPG as it was redundant. Baseline is already defined in section 1.1
 
Section 2.1.5 redefined age classification based on tertiles
 
Section 2.1.6 redefined exposure categories in months instead of weeks.
 
Section 2.2.1 Added table mentioning grouping for geographical regions
 
Section 2.2.2 Removed loss of glycemc control as primary endpoint; provided additional detail to used confirmation visit for time to initial treatment failure; Since we have only one primary endpoint, removed multiple testing methods section
 
Section 2.2.2.4 Added time to first treatment failure as supportive analysis; modified age categories for subgroup analysis; added smoking status, region and beta cell functional and insulin resistance as subgroups of interest; removed ethnicity
 
Section 2.2.3 Added rate of glycemc control over time as secondary endpoint; [REDACTED]

[figure not shown]
Version	Date	
		
analyzed and it is outside the scope of the SAP
 
Section 2.2.3.3 Added the analysis of rate of glycemic control over time in this section
 
Section 2.3 Removed analysis on AEs of run-in failure patients.
 
Section 2.3.5 Added clarification on using chi square test to compare events only if we have sufficient observed events.
 
Section 2.7 Updated power calculations based on single primary endpoint and updated yearly dropout rate.

Table of contents

Clinical Development	1
List of abbreviations	6
1 Definitions and general strategy	7
1.1 Baseline definitions	7
1.2 Last On-Treatment Observation (Endpoint Observation)	7
1.3 General data handling strategy	8
1.3.1 Output data precision	8
1.3.2 Efficacy Assessment Window / Week X Measurement	8
1.3.3 Laboratory visit windows.....	9
1.3.4 Multiple laboratory measurements within same day	10
1.4 Duration of exposure to study medication.....	10
1.5 Treatment-Emergent Adverse Events.....	10
1.6 Other clinically significant events (predefined AE risks).....	10
1.7 Hypoglycemic Event Classifications.....	11
1.8 Laboratory abnormalities.....	12
1.8.1 Clinically Significant Laboratory Abnormalities.....	12
1.8.2 Hepatic enzyme and CPK elevations	12

1.1 Baseline definitions

Unless specified otherwise, the baseline will be the measurement obtained on Day 1, or the closest sample obtained at an earlier visit (scheduled or unscheduled) to Day 1, if the Day 1 measurement is missing.

For derived variables [REDACTED] the baseline will be derived using measurements obtained on Day 1, or the closest samples obtained at an earlier visit (scheduled or unscheduled) to Day 1, if the Day 1 measurements are missing. Details of imputation methods to use if one or more of the individual measurements used in the derivation is missing, are detailed in [section 2.2.3.1](#).

Day 1 will be defined as the first day of study treatment (the earliest vildagliptin/placebo date as recorded on the vildagliptin/placebo dosage administration page of the eCRF).

Vital Signs

For blood pressure and pulse, baseline will be defined as the average of all pre-treatment visits, regardless of being scheduled or unscheduled. [REDACTED]

Routine ECG Measurements

ECGs are analyzed and interpreted locally for this study, hence only qualitative ECG measurements are recorded. ECGs are scheduled to be measured at screening (and not Day 1). Baseline is therefore defined as the measurement obtained at screening, unless there is a later, unscheduled measurement on or before Day 1 (in which case the latest of these will be used).

1.2 Last On-Treatment Observation (Endpoint Observation)

For specified efficacy variables, clinical laboratory variables, vital signs and ECG findings, the measurement obtained at the last post-baseline study visit will be considered the last on-treatment (endpoint) observation, regardless of whether it is obtained at a scheduled or unscheduled visit, up to the last scheduled visit.

For specified efficacy variables, clinical laboratory variables and ECG findings, end of Period 1 and end of Period 2 endpoints will also be of interest. The end of Period 1 endpoint is defined as the final available post-randomization assessment obtained at any visit (scheduled or unscheduled), prior to or at initial treatment failure, up to the last scheduled study visit. The end of Period 2 endpoint is defined as the final available post-randomization assessment

obtained at any visit (scheduled or unscheduled), prior to or at the initiation of insulin therapy, up to the last scheduled study visit.

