5.5.12 Early study termination

The study can be terminated at any time for any reason by Novartis. Should this be necessary, the patient should be seen as soon as possible and treated as described in [Section 6](#) for a prematurely withdrawn patient. The investigator may be informed of additional procedures to be followed in order to ensure that adequate consideration is given to the protection of the patient's interests. The investigator will be responsible for informing institutional review boards (IRBs) and/or independent ethics committees (IECs) of the early termination of the study.

6 Visit schedule and assessments

Visits are scheduled as indicated in [Table 6-1](#) & [Table 6-2](#). An "X" in [Table 6-1](#) & [Table 6-2](#) indicates which assessments are to be performed during each visit.

Patients who discontinue study drug before completing the study, and those who prematurely withdraw from the study for any reason, should be scheduled for a visit as soon as possible, at which time all of the assessments listed for the final visit (Visit 23) will be performed. At a minimum, they will be contacted for safety evaluations during the 30 days following the last intake of study drug, including final contact at the 30-day point. Documentation of attempts to contact the patient should be recorded in the source documents.

Table 6-1 Assessment schedule (year 1-2)

Visit	1	2	3	4	5	6	7	8	9	10	11
Week	-5	-3	BL	13	26	39	52	65	78	91	104
Assessments											
Screening log (see Section 6.1)		X									
Informed consent	S										
Inclusion/exclusion criteria (see Section 4.1 & Section 4.2)	S	S									
Demography (see Section 6.2)	X										
Medical history/current conditions	X										
Smoking history	X										
History of diabetes & complications	X										
Hepatitis screen (see Section 6.5.4)	X										
TSH (see Section 6.5.4)	X										
Serum pregnancy test (see Section 6.5.8)	X		X								
Physical examination (see Section 6.5.1)	S										
Randomisation			S								
Efficacy											
HbA1c (see Section 6.4.1)	X	X	X	X	X	X	X	X	X	X	X
FPG (see Section 6.4.2)	X	X	X	X	X	X	X	X	X	X	X
Fasting insulin (see Section 6.4.2)			X				X				X
Safety											
Vital signs including height (see Section 6.5.2)	X										
Vital signs (see Section 6.5.2)		X	X	X	X	X	X	X	X	X	X
ECG											
ECG (see Section 6.5.7)	X						X				X
Hematology (see Section 6.5.4)	X		X				X				X
Chemistry (see Section 6.5.4)	X		X				X				X

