9.5.3 Safety variables

[figure not shown]
The safety and tolerability of vildagliptin 50mg bid as add-on to metformin over 5-years of treatment will be compared to placebo as add-on to metformin based on data collected during the randomised treatment period in SAF set.

The assessment of safety will be based mainly on the frequency of treatment emergent AEs (including overall AEs), SAEs, death, AEs leading to study discontinuation or study drug interruption & pre-specified AE risks on the number of post BL laboratory values that fall outside of pre-determined ranges and on the frequency and severity of hypoglycemic events during the randomised treatment period. Summaries for safety assessment will be presented for the SAF set. Unless specified otherwise, comparison will be made to BL, which will be the measurement taken at Visit 3, or the sample obtained at an earlier visit (scheduled or unscheduled) which was closest to Day 1 if Day 1 measurement is missing.

AEs will be summarised by presenting, for each treatment group (vildagliptin 50mg bid + metformin, placebo + metformin), the number and percentage of patients having any AE, having an AE in each primary SOC and having each individual AE. Any other information collected (e.g. severity or relatedness to study medication) will be presented as appropriate.

[figure not shown]
Laboratory data will be summarised by presenting summary statistics of raw data and change from BL values (means, medians, standard deviations, ranges) and by presenting the number and percentage of patients having notable lab values or having endpoint change from BL meeting pre-specified percent change criteria. The identification of notable values will be based on the pre-specified criteria provided in the investigator binder (will also be included in the analysis plan). The predefined categories of liver enzyme (ALT/AST) and CPK elevations and persistent elevations will be summarised by treatment.

Hypoglycemia events will be included in all AE summaries. In addition, events will be characterised by event profile, such as ability to self-treat, self monitoring of plasma glucose level, precipitating event, time from last meal, time from last dose, and time of the day.

[figure not shown]
Data from other tests (e.g. vital signs including [redacted], ECGs) will be summarised as appropriate, incidences of notable values will be presented in the tables and notable values will be flagged in the listings.

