2.3.4 Electrocardiograms (ECGs)

Overall interpretation and details of abnormalities are collected at Screening and selected visits.

Change from the baseline ECG result to the endpoint (End of Period 1, End of Period 2, End of Study) ECG result will be summarized by a shift table. The number of patients with clinically significant abnormalities or not at baseline and at each endpoint ECG assessment will be tabulated.

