2.3.3 Vital signs

Baseline and endpoint values for blood pressure (sitting), and pulse (sitting) will be presented. Summary statistics for vital signs data will be presented by study visit. The summary by study visit will include only values obtained at the scheduled visit.

The number of patients with notably abnormal vital signs [REDACTED] post-baseline will be presented. This summary will be repeated for abnormalities occurring in Period 1. The criteria for notable abnormalities (see [Section 1.9](#)) will be listed.

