2.3.4 Electrocardiograms (ECGs)

Overall interpretation and details of abnormalities are collected at Screening and selected visits.

Change from the baseline ECG result to the endpoint (End of Period 1, End of Period 2, End of Study) ECG result will be summarized by a shift table. The number of patients with clinically significant abnormalities or not at baseline and at each endpoint ECG assessment will be tabulated.

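### SAP 2.3.4 tabulates ECGs only at period endpoints, so an abnormality seen at an earlier ECG and gone by the endpoint enters no ECG table

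*SAP*

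**What the plan says.** **ECG outputs.** SAP 2.3.4 plans two, worded the same in V3.0 and Addendum 1. The first is a shift table: "Change from the baseline ECG result to the endpoint (End of Period 1, End of Period 2, End of Study) ECG result will be summarized". The second is a count: "The number of patients with clinically significant abnormalities or not at baseline and at each endpoint ECG assessment will be tabulated".

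**Endpoint definition.** SAP 1.2 supplies it. For end of study, it says that for "vital signs and ECG findings, the measurement obtained at the last post-baseline study visit will be considered the last on-treatment (endpoint) observation". For the first period, "The end of Period 1 endpoint is defined as the final available post-randomization assessment obtained at any visit", up to initial treatment failure. End of Period 2 works the same way, up to the start of insulin. Scheduled and unscheduled visits both qualify.

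**Schedule.** Protocol Tables 6-1 and 6-2 place ECGs at screening and at Weeks 52, 104, 156, 208 and 260. SAP 1.1 takes the screening ECG as baseline unless a later one exists on or before Day 1.

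**Protocol commitment.** Protocol 9.5.3, on data from other tests and with ECGs named as an example, says "incidences of notable values will be presented in the tables" and that notable values will be flagged in listings.

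**Other safety data in the SAP.** SAP 2.3.2.1 and 2.3.2.2 count patients with notable hematology or biochemistry values at any post-baseline time. SAP 2.3.3 does the same for vital signs ("The number of patients with notably abnormal vital signs" post-baseline) and adds by-visit summaries. All of these counts are repeated for Period 1.

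**The concern.** An endpoint table shows the state at one moment. It does not show how many patients developed an abnormality during treatment. A patient with a clinically significant finding at Week 104 and a normal tracing at Week 260 appears as normal at baseline and normal at endpoint. The visible text of SAP 2.3.4 has no by-visit table, no any-time count and no listing that would show the Week 104 result.

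This matters most in Period 1, the only period in which vildagliptin is compared with placebo. After failure both arms receive vildagliptin. The SAP plans no Period 1 ECG incidence, although it plans one for laboratory values and vital signs.

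**Working it through.** The plan gives no figure of its own on this point. The check is a count, followed by the share of patients to whom the extreme case applies.

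**1. How many scheduled ECGs reach a table**

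Scheduled on-treatment ECGs: Weeks 52, 104, 156, 208, 260, which is 5. Each endpoint selects the latest ECG on or before its cut-off.

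| Patient (completes Week 260) | End of Period 1 | End of Period 2 | End of study | Distinct ECGs tabulated |
|---|---|---|---|---|
| Never fails, no insulin | 260 | 260 | 260 | 1 of 5 |
| Fails at Week 65, no insulin | 52 | 260 | 260 | 2 of 5 |
| Fails at Week 65, insulin at Week 117 | 52 | 104 | 260 | 3 of 5 |

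There are three endpoints, so 3 is the maximum. Enumerating all failure visits from Week 26 and all later insulin dates gave only 1, 2 or 3. At least 2 of the 5 scheduled ECGs are therefore always left out for a completer.

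**2. Share of patients who complete five years without failure**

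Inputs from Protocol 9.6 and SAP 2.7:
- 10% early failure by Week 13 in each arm
- 7.1% yearly failure on metformin
- hazard ratio 0.75
- yearly dropout 11% (Protocol 9.6 and SAP Addendum 1) or 4% (SAP V3.0)

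Assumptions added here: constant hazard after Week 13, and dropout independent of failure.

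- Yearly hazard on metformin: λ = −ln(1 − 0.071) = 0.0737. On the combination: 0.75 × λ = 0.0552.
- No failure in 5 years = 0.9 × exp(−hazard × 4.75).
  - Metformin: 0.9 × 0.705 = 63.4%
  - Combination: 0.9 × 0.769 = 69.2%
- No dropout in 5 years: 0.89⁵ = 55.8%; 0.96⁵ = 81.5%.

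| Yearly dropout | Metformin | Combination |
|---|---|---|
| 11% | 0.634 × 0.558 = 35% | 0.692 × 0.558 = 39% |
| 4% | 0.634 × 0.815 = 52% | 0.692 × 0.815 = 56% |

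**3. Share of abnormalities missed in that group**

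The documents say nothing on how long ECG abnormalities last, so this is a range.
- Present at one ECG only, each of the five equally likely: 4/5 = 80% missed.
- Lasting two consecutive ECGs, onset equally likely at each of the five: 3/5 = 60% missed. Counting only runs that lie wholly within the schedule gives 3/4 = 75%.
- Persisting to the last ECG: 0% missed.

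**The case against.** **Adverse events give another route.** Protocol 7.1 makes a test result an adverse event when it is considered clinically significant, and the SAP tabulates all adverse events overall and by period. This stands. A reader might infer that an abnormality disappears from the whole report, and the documents do not support that. The route is uncertain, though. Protocol 6.5.7 sends clinically significant ECG findings to the ECG evaluation page and the medical history page, and does not name the adverse event page. Protocol 6.5.1 does name it for physical findings made after the start of study drug.

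**The protocol commitment still holds.** SAP section 2 says the data will be analyzed according to protocol section 9, and the visible text of SAP 2.8 does not withdraw the ECG incidence. This also stands, and it supports adding the table. No notable ECG criterion is given, and the readings are qualitative and local. The comparison with numeric laboratory and vital-sign thresholds is therefore not exact, but the investigator's judgement of clinical significance can be counted at any visit.

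**The size can be overstated.** A reader might infer that 80% of abnormalities are missed, or that about two thirds of patients have only one ECG tabulated. The first needs abnormalities confined to a single ECG. The second uses non-failure before dropout, whereas the 1-of-5 count requires five-year completion. Patients who stop early are also due the Visit 23 assessments, which include an ECG.

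**ECG is not a leading safety variable.** Protocol 6.5 does not list it among the endpoints for the safety objective, and SAP 2.3 does not list it among the key safety variables. Amendment 3 concerns adjudicated cardiovascular events, not routine tracings. This limits the importance of the point but does not explain the omission.

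**Conclusion.** The point holds for the ECG tables. Both SAP versions tabulate ECGs only at the last available record for each endpoint: 1 of 5 scheduled on-treatment ECGs for a completer without failure, and at most 3 of 5 for any completer. These counts follow directly from the schedule and the definitions.

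The completer without failure describes about 35% (metformin) and 39% (combination) of patients at 11% yearly dropout, or 52% and 56% at 4%. These shares rest on the plan's failure inputs, a constant hazard and independent dropout. How many abnormalities go uncounted depends on their duration, and is zero for those lasting to the last ECG.

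The plan falls short of the incidence summary in Protocol 9.5.3 and is inconsistent with the SAP's counts for laboratory values and vital signs. A reader might go further and conclude that a treatment difference in ECG abnormalities would be missed altogether. The documents do not show that, because the adverse event tables may capture it. They do not guarantee it either. The primary analysis is unaffected.

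**What to change.** Add to SAP 2.3.4 the number and percentage of patients with a clinically significant ECG abnormality that was not present at baseline and occurs at any post-baseline ECG, scheduled or unscheduled. Show it overall and for Period 1, and add a patient listing. State the denominator for Period 1, because a patient who fails before Week 52 has no scheduled ECG in that period. Keep the endpoint shift table as it is.

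Reconcile Protocol 6.5.7 with 7.1 on where a clinically significant ECG finding made after the start of treatment is recorded.

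Cost: SAP wording and one or two tables from data already collected. The small downside is that some transient findings will be counted.
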